4.11 Storage and analysis of clinical samples: N/A

4.12 End of trial: N/A

5 TRIAL TREATMENTS

5.1 Name and description of intervention(s) under investigation

We will use the Neuroelectrics StarStim tDCS device (Figure 1) and the Flow Neuroscience Flow tDCS device (Figure 2). The tDCS device consists of two electrodes through which the stimulation is applied (anode electrode) and through which the stimulation is returned (cathode electrode), which creates a circuit.

In the StarStim tDCS device, the electrodes are fitted within a flexible neoprene cap, and there are different cap sizes (small, medium, large) to account for different head sizes. There are additional spaces within the cap through which the EEG acquisition can be made.

The Flow tDCS device consists of an adjustable headset with the tDCS electrodes built in.

5.2 Regulatory status of the drug (if applicable): N/A

5.3 Product Characteristics:

The Neuroelectrics StarStim tDCS device does not have CE mark approval for the treatment of major depression. The Soterix tDCS device is a similar device which has CE mark approval for the treatment of major depression (Figure 3).

However, the Soterix tDCS device does not incorporate the EEG electrodes within the device, in contrast to the Neuroelectrics Starstim tDCS device which provides a combined tDCS and EEG system within a simply designed, soft neoprene cap.

The Neuroelectrics Starstim tDCS device is portable and provides an ease of use in a simple design which allows EEG acquisition, which will facilitate its use in the community. The Flow tDCS device is portable and commercially available. Both devices can be programmed to provide the specific stimulation parameters for the study. The primary outcome of the study is to assess the feasibility and acceptability of tDCS sessions within the community.

Clinical efficacy of tDCS treatment for major depression

depression is not the primary outcome for the present study, which is not powered to investigate efficacy. The findings from the present study will be applied to design a multi-site randomised sham-controlled clinical trial, which will be powered to investigate efficacy.

5.4 Drug storage and supply (if applicable): N/A

5.5 Preparation and labelling of Investigational Medicinal Product (if applicable): N/A

5.6 Dosage schedules:

The electrodes will be placed in a bifrontal montage, in which the anode is placed over the left dorsolateral prefrontal cortex (DLPFC) and the cathode is placed over the right DLPFC. This is

[figure not shown]
Figure 1. StarStim tDCS device

Figure 2. Flow tDCS device

Figure 3. Soterix tDCS device

equivalent to the EEG positions at F3 and F4, respectively. The stimulation will be 2 mA, and the electrode area is 35 cm².

Participants will receive a 6-week course of active tDCS treatment, consisting of 5 sessions per week for the first 3 weeks followed by 2 sessions per week for 3 weeks, for a total of 21 tDCS sessions. The duration of each session is 30 minutes.

The tDCS parameters are based on meta-analyses (Meron et al., 2015; Brunoni et al., 2016; Mutz et al., 2018) which demonstrate that treatment effects are most evident at 2 mA current of 30 minute stimulus duration for 21 sessions for participants with recurrent major depression.

During the first session, participants will be taught by the study team how to fit the cap and deliver the tDCS treatment to themselves. During each session, the participant will be seated comfortably, and the research assistant will provide a discreet presence without interacting with the participant. The research assistant will supervise sessions either in person or via video link. Research assistants and participants will wear appropriate PPE during any sessions conducted at the study site or where the research assistant is present in person.

5.7 Dosage modifications: N/A

5.8 Known drug reactions and interaction with other therapies: N/A

5.9 Concomitant medication

If a participant wishes to begin another treatment while taking part in the study, we will continue with the tDCS treatment and we will continue with their follow up care.

5.10 Trial restrictions

There are no known contraindications whilst on the active phase of the trial including dietary requirements or restrictions.

5.11 Assessment of compliance with treatment

The tDCS device records the duration of each session, and there is an automatic shut-off to prevent unsafe use. The equipment will be programmed to provide only the type of stimulation, intensity and session length that are specified in the protocol. The placement is determined by the location of the electrodes which are fitted to specific locations in the cap. The research assistant will be present at each session, in person or via video link, in order to aid in the initial positioning and to monitor for any adverse events.

5.12 Name and description of each Non-Investigational Medicinal Product (NIMP): N/A

6 RECORDING AND REPORTING OF ADVERSE EVENTS

6.1 Definitions

Term	Definition
Adverse Event (AE)	Any untoward medical occurrence in a participant to whom an intervention has been administered, including occurrences which are not necessarily caused by or related to the intervention.
Adverse Reaction (AR)	An untoward and unintended response in a participant to an intervention which is related to any dose administered to that participant.

	
The phrase "response to an intervention" means that a causal relationship between an intervention and an AE is at least a reasonable possibility, i.e. the relationship cannot be ruled out.
 
All cases judged by either the reporting medically qualified professional or the Sponsor as having a reasonable suspected causal relationship to the intervention qualify as adverse reactions.

Serious Adverse Event (SAE)	
A serious adverse event is any untoward medical occurrence that:
 
 • results in death • is life-threatening • requires inpatient hospitalisation or prolongation of existing hospitalisation • results in persistent or significant disability/incapacity • consists of a congenital anomaly or birth defect 
Other 'important medical events' may also be considered serious if they jeopardise the participant or require an intervention to prevent one of the above consequences.
 
NOTE: The term "life-threatening" in the definition of "serious" refers to an event in which the participant was at risk of death at the time of the event; it does not refer to an event which hypothetically might have caused death if it were more severe.

Serious Adverse Reaction (SAR)	
An adverse event that is both serious and, in the opinion of the reporting Investigator, believed with reasonable probability to be due to the trial intervention, based on the information provided.

Suspected Unexpected Serious Adverse Reaction (SUSAR)	
A serious adverse reaction, the nature and severity of which is not consistent with the information about the intervention.

NB: to avoid confusion or misunderstanding of the difference between the terms "serious" and "severe", the following note of clarification is provided: "Severe" is often used to describe intensity of a specific event, which may be of relatively minor medical significance. "Seriousness" is the regulatory definition supplied above.

Detailed guidance can be found here:

http://ec.europa.eu/health/files/eudralex/vol-10/2011_c172_01/2011_c172_01_en.pdf

6.2 Operational definitions for (S)AEs

An SAE is any AE from this study that results in one of the following outcomes:

- death
- initial or prolonged inpatient hospitalization
- a life-threatening experience (that is, immediate risk of dying)
- persistent or significant disability/incapacity
- congenital anomaly/birth defect
- considered significant by the investigator for any other reason

Important medical events that may not result in death, be life-threatening, or require hospitalization may be considered serious adverse events when, based upon appropriate medical judgment, they may jeopardize the patient or subject and may require medical or surgical intervention to prevent one of the outcomes listed in this definition.

In all cases AEs and / or laboratory abnormalities that are critical to the safety evaluation of the participant must be reported to the Sponsor; these may be volunteered by the participant, discovered by the investigator questioning or detected through laboratory test or other investigation. Where certain AEs are not required to be reported to the Sponsor, these will still be recorded in the participant's medical records.

6.3 Recording and reporting of SAEs, SARs AND SUSARs

All serious adverse events will be recorded in the CRF as well as in the trial database, from which a line listing of SAEs can be extracted for review. The line-listing of SAEs will be reported to the Sponsor once per year.

All SAEs must be recorded on a serious adverse event (SAE) form. The CI/PI or designated individual will complete the Sponsor's SAE form and the form will be preferably emailed to the Sponsor within 5 working days of becoming aware of the event. The Chief or Principal Investigator will respond to any SAE queries raised by the Sponsor as soon as possible.

Where the event is unexpected and thought to be related to the intervention, this must be reported by the Investigator to the Health Research Authority within 15 days.

For each SAEs the following information will be collected:

- full details in medical terms and case description
- event duration (start and end dates, if applicable)
- action taken
- outcome
- seriousness criteria
- causality (i.e. relatedness to intervention), in the opinion of the investigator
- whether the event would be considered anticipated

6.4 Responsibilities

Principal Investigator (PI):

Checking for AEs and ARs when participants attend for tDCS sessions and at follow up.

1. Using medical judgement in assigning seriousness and causality and providing an opinion on whether the event/reaction was anticipated.
2. Ensuring that all SAEs are recorded and reported to the Sponsor.
3. Ensuring that AEs and ARs are recorded and reported to the Sponsor in line with the requirements of the protocol.

Chief Investigator (CI) / delegate:

1. Clinical oversight of the safety of patients participating in the trial, including an ongoing review of the risk / benefit.
2. Using medical judgement in assigning the SAEs seriousness, causality and whether the event was anticipated where it has not been possible to obtain local medical assessment.
3. Immediate review of all SUSARs.
4. Review of specific SAEs and SARs in accordance with the trial risk assessment and protocol.

Sponsor: (NB where relevant these can be delegated to CI)

1. Central data collection and verification of AEs, ARs, SAEs, SARs and SUSARs according to the trial protocol onto a database.
2. Reporting safety information to the CI, delegate or independent clinical reviewer for the ongoing assessment of the risk / benefit.
3. Notifying Investigators of SUSARs that occur within the trial.

6.5 Notification of deaths

All deaths, including deaths deemed unrelated to the study, will be reported to the Sponsor within 24 hours of notification.

6.6 Pregnancy reporting

All pregnancies within the trial (either the trial participant or the participant's partner, with participants consent) will be reported to the Principal Investigator and the Sponsor.

Pregnancy is not considered an AE unless a negative or consequential outcome is recorded for the mother or child/foetus. If the outcome meets the serious criteria, this would be considered an SAE.

6.7 Overdose: N/A

6.8 Reporting urgent safety measures

If any urgent safety measures are taken the Sponsor shall immediately and in any event no later than 3 days from the date the measures are taken, give written notice to the relevant REC of the measures taken and the circumstances giving rise to those measures.

6.9 The type and duration of the follow-up of participants after adverse reactions.

For 3 months after the last tDCS to the participants, adverse events and reactions be recorded and reported.

Any SUSAR will need to be reported to the Sponsor irrespective of how long after the reaction has occurred until resolved.

6.10 Development safety update reports

The Chief Investigator will provide Development Safety Update Reports (DSURs) once a year throughout the clinical trial, or as necessary, where relevant to the REC and the Sponsor.

The report will be submitted within 60 days of the Developmental International Birth Date (DIBD) of the trial each year until the trial is declared ended.

7 STATISTICAL ANALYSIS PLAN

7.1 Sample size calculation

We will enrol 30 participants with major depression based on a 20% attrition rate to achieve a sample size of 24 participants who will complete the course of treatment, given the exploratory nature of the pilot study.

[figure not shown]
7.2 Planned recruitment rate

The planned recruitment rate is 1-2 participant/s per month.

7.3 Statistical analysis plan

7.3.1 Summary of baseline data and flow of patients

Consort Flow Diagram:

7.3.2 Primary outcome analysis

The primary outcome analysis is participant retention which will be measured by the number of enrolled participants who do not drop out before the 6 week course of tDCS, divided by the total number of enrolled participants, expressed as a percentage.

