1.4 Primary endpoint/outcome

The hypothesis is that there will be participant retention of 70% or greater.

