1.7 Table of endpoints/outcomes

Objectives	Outcome Measures	Timepoint of evaluation of this outcome measure
Primary Objective To assess the feasibility of the present trial in terms of participant retention	Participant retention \geq 70%	End of tDCS sessions (visit 21)
Secondary Objective To assess the acceptability of the intervention	Positive endorsement of tDCS sessions as measured by an acceptability questionnaire	End of tDCS sessions (visit 21)

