4.10 Withdrawal criteria

Participants will be withdrawn from the trial if they do not comply with the intervention, namely if they are unable to have a minimum of 50% of the tDCS session (10 out of 21 sessions), or if they develop serious adverse effects from any part of the study. Recording of the reasons for withdrawal will be made. Their GP will be informed about their withdrawal, and there will have a telephone follow up at 1 month following their withdrawal.

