7.3.3 Secondary outcome analysis

The secondary outcome analyses will be the percentage of participants rating the intervention as acceptable at the end of the 6 week course of tDCS. The acceptability scale consists of the question 'How acceptable did you find the tDCS sessions?' with responses ranging from 'Very unacceptable' to 'Very acceptable' on a 7-point anchored Likert scale with the acceptable ratings being from rating 5-7.

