7.4 Subgroup analyses: N/A

7.5 Adjusted analysis: N/A

7.6 Interim analysis and criteria for the premature termination of the trial: N/A

7.7 Participant population

All participants will be included in the analysis in an intention to treat analysis and participants who have completed the study will be included in a completer analysis.

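### The primary outcome formula in 7.3.2 counts only drop-outs before the tDCS course, at odds with the visit 21 timepoint in 1.7 and the completion basis in 7.1, so read literally it misses losses during treatment

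*Combined protocol and SAP*

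**What the plan says.** Section 7.3.2 is the only place where the primary outcome is given as a formula. Its numerator is "the number of enrolled participants who do not drop out before the 6 week course of tDCS" and its denominator is all enrolled participants.

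Other sections place the outcome later:

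- The endpoint table in 1.7 gives the timepoint for this same outcome as "End of tDCS sessions (visit 21").
- Section 7.1 sets enrolment at 30 "based on a 20% attrition rate to achieve a sample size of 24 participants who will complete the course of treatment".
- Section 7.3.3, directly after the formula, takes the secondary outcome from participants "rating the intervention as acceptable at the end of the 6 week course of tDCS".

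Section 1.4 states the hypothesis that "there will be participant retention of 70% or greater". Section 1.3 describes the outcome as retention after enrolment and gives no end point. Section 4.10 provides for withdrawal because of missed sessions or serious adverse effects, so losses during the course are foreseen.

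**The concern.** The formula and the endpoint table stop the clock at opposite ends of the treatment period. Under 7.3.2 as written, a participant who attends one session and then leaves has not dropped out before the course, and so counts as retained. The quantity is then the proportion of enrolled participants who start treatment.

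The term *drop out* is also undefined. The formula does not say whether participants withdrawn by the trial under 4.10, or those who stop responding to contact, count as drop-outs.

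Retention is the primary objective and the only endpoint with a numerical target. Section 5.3 says that "The findings from the present study will be applied to design a multi-site randomised sham-controlled clinical trial". Tolerability of a 21-session, 6-week schedule shows mainly in who stays once treatment has begun. The literal formula cannot register those losses, however many there are.

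**Working it through.** **Inputs from the documents.** 30 enrolled, 20% attrition and 24 completers (7.1); target of 70% (1.4, 1.7); numerator and denominator (7.3.2); timepoint of visit 21 (1.7).

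**Assumed inputs.** The documents do not split attrition into losses before and during the course. All splits below, and the total attrition rates of 30% and 40%, are illustrations.

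**Step 1: the plan's own figure.** 24 / (1 − 0.20) = 30. The enrolment figure reproduces, with attrition counted up to completion of the course. On that basis planned retention is 24/30 = 80%.

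**Step 2: the target as a count.** 0.70 × 30 = 21 retained, so at most 9 losses.

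**Step 3: the two readings.** Let *a* be the number lost before the course and *b* the number lost during it.

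- Literal 7.3.2: (30 − a)/30
- Visit 21 basis: (30 − a − b)/30
- Difference: b/30, the proportion lost during the course

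| Lost before (a) | Lost during (b) | Literal 7.3.2 | Visit 21 | 70% met? (literal / visit 21) |
|---|---|---|---|---|
| 6 | 0 | 80% | 80% | yes / yes |
| 3 | 3 | 90% | 80% | yes / yes |
| 0 | 6 | 100% | 80% | yes / yes |
| 0 | 10 | 100% | 66.7% | yes / no |
| 1 | 11 | 96.7% | 60% | yes / no |
| 6 | 6 | 80% | 60% | yes / no |
| 9 | 3 | 70% | 60% | yes / no |
| 10 | 2 | 66.7% | 60% | no / no |

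**Step 4: when the conclusions differ.** The visit 21 basis misses the target if a + b ≥ 10. The literal formula misses it only if a ≥ 10. The two therefore disagree exactly when a + b ≥ 10 and a ≤ 9.

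**Step 5: chance of observing at least 21 of 30.** Binomial with n = 30, P(X ≥ 21), treating losses as independent. On the visit 21 basis, p is 1 minus total attrition. In the literal column half of those who leave are assumed to go before the course, so p is 1 minus half of total attrition.

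| Total attrition | Visit 21 basis | Literal, half of losses before the course |
|---|---|---|
| 20% | p = 0.80: 0.939 | p = 0.90: 1.000 |
| 30% | p = 0.70: 0.589 | p = 0.85: 0.990 |
| 40% | p = 0.60: 0.176 | p = 0.80: 0.939 |

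If all losses occur before the course, the two columns coincide.

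**The case against.** The strongest reply is that this is a slip of the pen. Protocol and SAP are one document, 1.7 states the timepoint outright, 7.1 and 7.3.3 point the same way, and a sensible analyst would use visit 21. At the planned 20% attrition the 70% target is met on either reading. The 70% is a hypothesis with no progression rule attached. Section 7.1 is a planning assumption about completers and does not define retention, so only 1.7 contradicts the formula directly. Losses by stage may also appear elsewhere: section 7.7 says that "participants who have completed the study will be included in a completer analysis", section 4.10 that "Recording of the reasons for withdrawal will be made", and section 7.3.1 plans a CONSORT flow diagram. (The diagram and Appendix 2 could not be seen in the text available.) Finally, loss to follow-up is described in 4.8 only for the 3- and 6-month assessments, after visit 21.

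Much of this is fair. A slip is the likeliest explanation, the conflict with 7.1 is indirect, and reversal of the conclusion is a possibility that depends on attrition well above plan. But 7.3.2 is the operative definition of the primary outcome, and a reader has to override it by inference from other sections. The other outputs may reveal mid-course losses, but they do not alter the headline percentage or its comparison with 70%. That loss to follow-up is mentioned only after treatment leaves open how a participant who falls out of contact during the course is counted.

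**Conclusion.** The concern holds: the primary outcome formula is wrong as written. It conflicts directly with the timepoint in 1.7, does not match the completion basis of the attrition in 7.1, and omits every loss during treatment.

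At the planned attrition the effect is on the reported figure, by up to 20 percentage points (100% against 80%), and not on whether 70% is reached. The conclusion can reverse only if 10 or more of 30 leave in total and 9 or fewer of them leave before the course. At an assumed 40% attrition with half of the losses before treatment, the chance of meeting the target rises from 0.18 to 0.94. These sizes rest on assumed splits and, above 20%, assumed rates. The contradiction itself needs no assumption.

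**What to change.** In 7.3.2, define retention as enrolled participants who remain in the trial at visit 21 (end of the 6-week course), divided by all enrolled. State that anyone who dropped out, was withdrawn under 4.10 or was lost to follow-up between enrolment and visit 21 counts as not retained. This brings the formula into line with 1.7.

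Being in the trial at visit 21 is not the same as having completed the course. Report the number completing the course, which is the basis of 7.1, next to the retention figure, and state how completion is counted.

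The cost is one or two sentences of SAP wording, with no new data. If the team always meant visit 21, the retention figure does not change. If it would have applied the formula as written, the reported retention may be less favourable.

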7.3.3 Secondary outcome analysis

The secondary outcome analyses will be the percentage of participants rating the intervention as acceptable at the end of the 6 week course of tDCS. The acceptability scale consists of the question 'How acceptable did you find the tDCS sessions?' with responses ranging from 'Very unacceptable' to 'Very acceptable' on a 7-point anchored Likert scale with the acceptable ratings being from rating 5-7.

7.4 Subgroup analyses: N/A

7.5 Adjusted analysis: N/A

7.6 Interim analysis and criteria for the premature termination of the trial: N/A

7.7 Participant population

All participants will be included in the analysis in an intention to treat analysis and participants who have completed the study will be included in a completer analysis.

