1.6 Exploratory endpoints/outcomes

Exploratory measures:

- i. Trained rater measure of depressive symptoms: Hamilton Rating Scale for Depression (HRSD): The hypothesis is that course of tDCS treatment will improve clinical response as measured by a HRSD score reduction of $\geq 50\%$ following the course of tDCS treatment.
- ii. Self-report measure of depressive symptoms: Patient Health Questionnaire (PHQ-9)
- iii. Trained rater measure of anxiety symptoms: Hamilton Anxiety Scale (HAMA)
- iv. Trained rater measure of manic symptoms: Young Mania Rating Scale (YMRS)
- v. Self-report measure of disability and impairment: Sheehan Disability Scale (SDS)
- vi. tDCS Adverse Events Questionnaire (AEQ)
- vii. Participant acceptability questionnaire scales
- viii. Optional EEG recordings during an eyes-closed resting state for 10 minutes followed by a decision making task (eg. Cheng and Lee, 2015) and an emotional valence categorisation task (eg. Maeoka et al., 2012).

Exploratory outcomes:

- 1) HRSD reduction $\geq 50\%$ following the course of tDCS
- 2) HRSD score ≤ 7 following the course of tDCS
- 3) Improvement in self-reported depressive symptoms as measured by PHQ-9
- 4) Improvement in anxiety symptoms as measured by HAMA
- 5) No significant increase in manic symptoms as measured by YMRS
- 6) Improvement in disability experience as measured by SDS
- 7) Recording of adverse events as measured by the tDCS AEQ
- 8) Measure of neural connectivity using resting state EEG, which has been proposed as potential surrogate outcome measure for clinical applications (Alhaj et al., 2011; Miniussi et al., 2012; Woods et al., 2016). Quantitative EEG analysis of the decision making task (eg. Cheng and Lee, 2015) and emotional valence categorisation task (eg. Maeoka et al., 2012).

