4.3 The randomisation scheme: N/A

4.3.1 Method of implementing the randomisation/allocation sequence: N/A

4.4 Blinding: N/A

4.5 Emergency Unblinding: N/A

4.6 Baseline data

The baseline data consist of: HRSD, PHQ-9, HAMA, YMRS, SDS, tDCS AEQ, Acceptability questionnaire, EEG (optional) (Appendix 2).

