7.8 Procedure(s) to account for missing or spurious data

Any missing data will be imputed in a last observation carried forward model.

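### Sections 7.7 and 7.8 define no treated-participant set and do not exempt the AEQ from LOCF, so the exploratory adverse-event outcome need not describe those who received tDCS

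*Combined protocol and SAP*

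**What the plan says.** All references are to the combined protocol and SAP.

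- **Analysis sets (7.7).** The rule is "All participants will be included in the analysis in an intention to treat analysis", with a second analysis of those who completed the study. No other set is defined.
- **Missing data (7.8).** "Any missing data will be imputed in a last observation carried forward model". No outcome is exempted.
- **The outcome (1.6).** Exploratory outcome 7 is "Recording of adverse events as measured by the tDCS AEQ". Section 7.3 describes analyses for retention and acceptability only, so outcome 7 has no stated rate, unit or denominator of its own and falls under the general rules in 7.7 and 7.8.
- **Who can have an adverse event (6.1).** The definition is "Any untoward medical occurrence in a participant to whom an intervention has been administered", with or without a causal link.
- **Baseline (4.6).** The AEQ is listed among the baseline measures.
- **Numbers (7.1, 5.6).** "We will enrol 30 participants with major depression based on a 20% attrition rate", to leave 24 who complete. The course is 21 sessions.
- **Schedule.** AEQ timing is in Appendix 2 (cited in 4, 4.6 and 4.7), which is not in the text supplied.

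**The concern.** Adverse events are normally summarised among people exposed to the intervention, and the definition in 6.1 points the same way. Neither set in 7.7 is that group. Three things follow if 7.7 and 7.8 are applied literally to the AEQ.

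1. Someone who enrols but leaves before the first session adds one to the denominator without having been at risk from stimulation. If that person has a baseline AEQ, LOCF turns it into an on-treatment score.
2. Someone who stops mid-course has no later stimulation to rate, yet the last AEQ is repeated at each later AEQ time point. These values are not missing observations of something that happened: the session did not take place.
3. The completer set does not repair this. Section 4.10 withdraws participants who develop serious adverse effects, so that set leaves out some of the people with the events of interest.

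Section 5.3 says the findings will be used to design a multi-site sham-controlled trial. Tolerability per treated person is a natural input to that design, and the stated rules do not produce it.

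**Working it through.** **Inputs.** Enrolled 30, completers 24, attrition 20% (7.1). Sessions per participant 5 × 3 + 2 × 3 = 21 (5.6), so 30 × 21 = 630 planned. The documents do not give the number who leave before session 1 (k), the sessions attended by other dropouts, the AEQ schedule or any expected event rate. These are assumptions below, shown as ranges.

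**Plan's own figure.** 24 / (1 − 0.20) = 30. It reproduces exactly, with 30 − 24 = 6 expected losses.

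**Person level.** If never-treated enrolees count as event-free, then

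all-enrolled rate = treated rate × (30 − k) / 30.

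| k | Treated | Factor | All-enrolled rate if treated rate is 30% (assumed) |
|---|---|---|---|
| 0 | 30 | 1.000 | 30% |
| 1 | 29 | 0.967 | 29% |
| 3 | 27 | 0.900 | 27% |
| 6 | 24 | 0.800 | 24% |

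The relative understatement is therefore 0% to 20%. For an event seen in nobody, the one-sided 95% upper limit is 1 − 0.05^(1/n): 9.5% with n = 30 and 11.7% with n = 24.

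The direction reverses if a never-treated enrolee's baseline AEQ is positive for the symptom and is carried forward. With k = 3, a treated rate of 30% and all three baselines positive, the rate is (0.30 × 27 + 3) / 30 = 11.1 / 30 = 37%.

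**Session level, assuming an AEQ is due at every session.** Undelivered sessions for six dropouts = 6 × (21 − sessions attended):

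- none attended: 126 / 630 = 20.0%
- leave after 5: 96 / 630 = 15.2%
- leave after 20: 6 / 630 = 1.0%

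Take the middle case. Delivered sessions are 24 × 21 + 6 × 5 = 534. Let p be the rate over delivered sessions. LOCF fills 96 values with the six people's last answers:

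| p | All six last answers negative | All six last answers positive |
|---|---|---|
| 10% | 53.4 / 630 = 8.5% | (53.4 + 96) / 630 = 23.7% |
| 30% | 160.2 / 630 = 25.4% | (160.2 + 96) / 630 = 40.7% |

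These are bounds for that scenario, not predictions. They show that the direction is not fixed.

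**If the AEQ is collected at only a few visits.** The session figures no longer apply, but an end-of-course AEQ would still be imputed for up to 6 / 30 = 20% of participants.

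**The case against.** The strongest reply is that the plan never states an adverse-event rate. Outcome 7 is worded as recording events, and 7.3 is silent on it. A reader might infer that the plan calculates a diluted rate; it does not. Dilution is what the general rules would produce if applied, and a sensible analyst might use treated participants anyway. This stands as a limit on the claim. It does not remove the point, because 7.7 and 7.8 are stated in terms that cover everyone and any missing value, and nothing narrower is offered.

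Other objections also have force:

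- A reader might infer from 6.1 that the AEQ can be scored only in people and sessions that received stimulation. Section 4.6 contradicts that by listing it at baseline. The definition in 6.1 governs adverse events, not who may fill in the form.
- The split of the six losses is unknown. If every dropout had at least one session, the person-level dilution is zero.
- For a count of people who ever reported an effect, repeating a treated person's last answer adds nobody new. For treated participants, LOCF therefore affects only summaries by session or time point.
- Session-level imputation depends on Appendix 2, and so does whether the baseline AEQ precedes the first stimulation.
- A reader might infer that adverse-event stoppers are lost from the analysis altogether. They are not: the completer analysis supplements the all-participant analysis, which keeps them. The completer set also omits non-completers of every kind.
- The trial is small. The exact 95% interval for 8 of 30, for example, is about 12% to 46%, wider than the shift from a changed denominator. That is a fair comment on importance, though imprecision is no reason to keep the wrong denominator.

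**Conclusion.** The point holds in a limited form. Sections 7.7 and 7.8, followed literally for the AEQ, provide no set of treated participants and fill AEQ time points that did not take place. The person-level effect is a relative understatement of 0% to 20%, assuming 0 to 6 never-treated enrolees of 30 who are counted as event-free. The 20% end requires all six expected losses to occur before session 1. The LOCF effect has no fixed direction, and its size depends on the AEQ schedule and on dropout timing, neither of which the documents supplied give.

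The consequences are bounded. The outcome is exploratory, and nothing in the documents makes the AEQ rate the trial's main safety result. Recording and reporting of serious adverse events in section 6 runs separately. Retention and acceptability do not depend on this point. The change is still worth making, because the present rules give a worse summary than data already collected would allow.

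**What to change.** - **In 7.7**, add a safety set: all participants who started at least one tDCS session, whether or not it was completed. Report AEQ results and other adverse events in this set as the number of participants with each event out of those treated. Where the AEQ is collected per session, also report events per session delivered, taking delivered sessions from the device record described in 5.11.
- **In 7.7 or 7.3**, state that the baseline AEQ is shown separately and is not counted as an on-treatment result.
- **In 7.8**, exempt the AEQ and adverse events from LOCF. No value is generated for a session or visit that did not take place.
- **Leave retention unchanged**: all enrolled participants remain its denominator (7.3.2).

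The cost is a few sentences and one extra denominator, with no new data collection. The stated adverse-event rate per person may come out slightly higher.
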